5.2. Determination of Sample Size

The study design requires 6 patients at each cohort in Part A for assessing the DLTs observed. This sample size was not based on a statistical power calculation.

In Part B, 6 patients are needed to evaluate PK and safety profile of olaratumab monotherapy. This sample size was estimated empirically based on other Phase 1 oncology studies. The estimation precision of PK parameters in this study is expected to be similar to that in previous studies (Study JGDC and Study JGDF), although there are no inter-subject variability data on a new assay.

5.3. Method of Assignment to Treatment

Patients who meet all criteria for enrollment will be assigned to receive olaratumab in combination with doxorubicin (Cohort 1 or Cohort 2 in Part A) or olaratumab monotherapy (Part B), at the investigator's discretion. Before each patient's enrollment into the study, an eligibility check must be conducted at the investigational site to confirm that each patient meets all enrollment criteria. Upon confirmation of eligibility, the sponsor or designee will confirm the dose and identification number assignment for each patient. Initiation of Cohort 2 refers to Section 7.2.1.4 in the protocol.

6. A Priori Statistical Methods

6.1. General Considerations

Statistical analysis of this study will be the responsibility of Eli Lilly Japan K.K. Pharmacokinetic analyses will be planned separately from this SAP.

6.1.1. Analysis Populations

The Analysis populations are defined as follows:

- **Enrolled Population:** Anyone who signed the informed consent and who was confirmed to be eligible and have been assigned to a treatment will be included in this population.
- **FAS Population:** All enrolled patients who received any amount of study drugs (either olaratumab or doxorubicin) will be included in the FAS Population. The FAS Population is based on the intent-to-treat principle and will be used for the analysis of baseline characteristics, efficacy data, safety data, and biomarkers.
- **DLT Population:** All enrolled patients who will complete Cycle 1 (initial 21-day treatment period), or who will discontinue due to DLT during Cycle 1, will be included in the DLT Population. Patients who will discontinue during Cycle 1 due to other reasons than DLT will be excluded from the DLT Population. The DLT Population will be used for summarizing a proportion of patients with DLT.

6.1.2. Data Analyses

All summary tables, figures and data listings will be produced by using the statistical packages SAS version 9.2 (or a more recent version).

Data will be summarized by part and cohort.

Baseline is defined as the last non-missing observation prior to the time of the first infusion of the study drug, unless otherwise stated. Observations on the same day of the first infusion of the study drug for which the time (hours and/or minutes) is missing and, according to the study schedule, to be collected prior to treatment, will also be considered baseline.

Descriptive statistics will include counts and percentages for categorical variables, and number of observations, mean, standard deviation, median, minimum and maximum for continuous variables unless otherwise stated.

Additional exploratory analyses of the data will be conducted as deemed appropriate.

The following data handling conventions will be applied in the analyses.

Study Day: Study day indicates the number of days the patient has been receiving study treatment. It is calculated as (assessment date)-(date of the first infusion of the study drug)+1 days if the assessment is done on or after the first infusion day of the study drug. If the assessment is done prior to the first infusion day of the study drug, study day will be calculated as (assessment date)-(date of the first infusion of the study drug). Date of the first infusion of the study drug is defined as study day 1.

6.2. Adjustments for Covariates

Adjustments for covariates will not be performed in any analysis of this study.

6.3. Handling of Dropouts or Missing Data

The birth date will be imputed by assigning month and day with July 1st to calculate age.

The following rules will be used for the imputation of incomplete initial pathological diagnosis date for the purpose of deriving duration of disease:

- If only the day of the month is missing, the 15th of the month will be used to replace the missing day.
- If both the day and the month are missing, July 1st will be used to replace the missing information.

Patient data listings will show partial dates without applying the above imputation rules.

In other measurement for efficacy and safety variables, the imputation for missing values will not be performed.

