Protocol I5B-JE-JGDK (b)

A Phase 1 Study of Olaratumab in Japanese Patients with Advanced Soft Tissue Sarcoma or Advanced Solid Tumors

NCT02377752

Approval Date: 28-Sep-2018

1. Protocol I5B-JE-JGDK (b)

A Phase 1 Study of Olaratumab in Japanese Patients with Advanced Soft Tissue Sarcoma or Advanced Solid Tumors

Confidential Information

The information contained in this protocol is confidential and is intended for the use of clinical investigators. It is the property of Eli Lilly and Company or its subsidiaries and should not be copied by or distributed to persons not involved in the clinical investigation of olaratumab (LY3012207), unless such persons are bound by a confidentiality agreement with Eli Lilly and Company or its subsidiaries. This document and its associated attachments are subject to United States Freedom of Information Act (FOIA) Exemption 4. Note to Regulatory Authorities: this document may contain protected personal data and/or commercially confidential information exempt from public disclosure. Eli Lilly and Company requests consultation regarding release/redaction prior to any public release.

Olaratumab (LY3012207)

This Phase 1 study is a multicenter, nonrandomized, open-label study to evaluate intravenous olaratumab in combination with doxorubicin in Japanese patients with advanced soft tissue sarcoma or advanced solid tumors (Part A), and intravenous olaratumab alone in Japanese patients with advanced solid tumors (Part B).

Eli Lilly Japan KK
Kobe, Hyogo, Japan

Protocol Approved by Lilly: 09 Dec 2014
Amendment (a) Protocol Electronically Signed and Approved by Lilly on 26 Jun 2015
Amendment (b) Protocol Electronically Signed and Approved by Lilly on date provided below.

Approval Date: 28-Sep-2018 GMT

2. Synopsis

Name of Investigational Product: Olaratumab	
Title of Study: A Phase 1 Study of Olaratumab in Japanese Patients with Advanced Soft Tissue Sarcoma or Advanced Solid Tumors	
Number of Planned Patients/Subjects: Enrolled: 24	Phase of Development: 1
Length of Study: First patient enrolled (assigned to therapy): March 2015 Estimated last patient visit: March 2019	

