6.1.1. Inclusion Criteria

Patients may be included in the study if they meet all of the following criteria during screening prior to first dose of study drug.

[1] Part A

Have histological or cytological evidence of a diagnosis of advanced or metastatic solid tumor, especially STS (other than Kaposi's sarcoma and gastrointestinal stromal tumors), which is not amenable to treatment with surgery or radiotherapy. The patient must be, in the judgment of the investigator, an appropriate candidate for olaratumab and doxorubicin therapy. Patients other than STS patients must be an appropriate candidate for olaratumab therapy in combination with doxorubicin after available standard therapies have failed to provide clinical benefit for their disease.

Part B

Have histological or cytological evidence of a diagnosis of solid tumor that is advanced or metastatic. The patient must be, in the judgment of the investigator, an appropriate candidate for olaratumab monotherapy after available standard therapies have failed to provide clinical benefit for their disease.

[2] Have the presence of measurable or nonmeasurable disease as defined by the Response Evaluation Criteria in Solid Tumors (RECIST) version 1.1 (Eisenhauer et al. 2009).

[3] Are ≥ 20 years of age.

[4] Have given written informed consent prior to any study-specific procedures.

[5] Have adequate organ and coagulation function, including:

- a. Hematologic: Absolute neutrophil count (ANC) $\geq 1.5 \times 10^9/L$, platelets $\geq 100 \times 10^9/L$, and hemoglobin ≥ 9 g/dL.
- b. Hepatic: Bilirubin ≤ 1.5 times the upper limit of normal (ULN) and ALT and aspartate aminotransferase (AST) $\leq 3.0 \times$ ULN.
- c. Renal: Serum creatinine $\leq 1.5 \times$ ULN. If creatinine is above the ULN, creatinine clearance is ≥ 45 mL/min ([Attachment 7](#)).
- d. Coagulation: international normalized ratio (INR) ≤ 1.5 and prothrombin time $\leq 1.5 \times$ ULN, if not receiving anticoagulation therapy. Patients on full dose anticoagulation must be on a stable dose of oral anticoagulant or low molecular

weight heparin, and if on warfarin must have therapeutic INR and have no active bleeding (defined as within 14 days prior to first dose of study medication) or pathological condition that carries a high risk of bleeding (eg, tumor involving major vessels or known varices)

- [6] Have an ECOG PS of ≤ 1 .
- [7] Have discontinued previous treatments for cancer and recovered from the acute effects of therapy.

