10.3. Patient Characteristics

Demographic and baseline characteristics (ie, age [years], age categories [<65 years vs. ≥ 65 years], gender, height [cm], weight [kg], and ECOG PS), pre-treatment disease characteristics (ie, cancer type, TNM staging at the time of diagnosis, sites of metastatic disease, and duration of disease [months from first confirmation of cancer to first dose]), prior anticancer treatments or surgery (ie, type of therapy, regimen, and prior surgery), and medical history will be summarized by part and cohort for the FAS Population.

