6.7. Patient Characteristics

For the FAS population, demographic and baseline disease characteristics will be summarized by part and cohort.

Demographic characteristics are as follows:

age (years), age categories (<65 years vs. ≥65 years), gender, race, height (cm), weight (kg), body surface area (m²) and Body Mass Index (kg/m²),

where body surface area is calculated using DuBois method; $0.007184 \times \text{weight}^{0.425} \times \text{height}^{0.725}$ and Body Mass Index = $\text{weight} / (\text{height} / 100)^2$.

Baseline disease characteristics are as follows:

Alcohol use, Tobacco use, Eastern Cooperative Oncology Group (ECOG) performance status, initial pathological diagnosis (or cancer type), disease stage at diagnosis, TNM at diagnosis, sites of Metastatic Disease, and duration of disease (months from the first confirmation of cancer to the first infusion)

In addition, prior anticancer treatments or surgery (radiotherapy, surgical procedure and systemic therapy), historical conditions and pre-existing conditions will be summarized by part and cohort.

Listings of demographic and baseline disease characteristics, of historical conditions and of pre-existing conditions also will be provided for the FAS population.

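### The diagnosis-date imputation in SAP 6.3 is not limited to the first infusion date, so a partial date in the year or month of first dosing can give a negative duration of disease

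*SAP*

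**What the plan says.** SAP 6.3 (Handling of Dropouts or Missing Data) introduces the rules by their purpose: "The following rules will be used for the imputation of incomplete initial pathological diagnosis date for the purpose of deriving duration of disease". There are two:

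- Day missing: "If only the day of the month is missing, the 15th of the month will be used to replace the missing day".
- Day and month missing: "If both the day and the month are missing, July 1st will be used to replace the missing information".

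The section adds that listings will show the partial dates as recorded. It closes with "In other measurement for efficacy and safety variables, the imputation for missing values will not be performed", which places no limit on the two rules above.

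The derived variable is defined in SAP 6.7 (Patient Characteristics) as "duration of disease (months from the first confirmation of cancer to the first infusion". Protocol 10.3 defines it in the same way: "duration of disease [months from first confirmation of cancer to first dose".

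Under SAP 6.1.2, continuous variables are reported by part and cohort with mean, standard deviation, median, minimum and maximum. SAP 5.2 and Protocol 10.1 plan 6 patients per cohort.

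**The concern.** The imputed date is set without reference to when the patient was first dosed. If the known part of the date is the same year or month as the first infusion, the fixed day can fall after that infusion, and the derived duration becomes negative.

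Such a value cannot be true. Protocol 6.1.1 makes tissue or cell evidence of the diagnosis an entry criterion, to be met in screening before the first dose.

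The case can arise under the entry criteria. In Part A, failure of standard treatment is asked only of patients without soft tissue sarcoma: "Patients other than STS patients must be an appropriate candidate for olaratumab therapy in combination with doxorubicin after available standard therapies have failed". No minimum time since diagnosis is stated, so a newly diagnosed sarcoma patient may enter. The protocol synopsis gives "First patient enrolled (assigned to therapy): March 2015", so dosing began in the half of the year in which the July rule fails.

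At stake is one line of the baseline table. In a cohort of about 6, one impossible value can become the printed minimum and pull the mean down.

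**Working it through.** The plan states no figure on this point, so there is none to reproduce. The check is date arithmetic.

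**Inputs.** Imputation days (15th; 1 July) from SAP 6.3; definition of duration from SAP 6.7 and Protocol 10.3; March 2015 as the month of first enrolment from the protocol synopsis; 6 patients per cohort from SAP 5.2. Assumption: one month is 30.4375 days, which does not affect the sign.

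**Formula.** Duration in months = (first infusion date - imputed diagnosis date) / 30.4375.

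**Results when the diagnosis falls in the year or month of first infusion.**

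| Recorded diagnosis | First infusion | Imputed date | Days | Months |
|---|---|---|---|---|
| 2015 | 1 Mar 2015 | 1 Jul 2015 | -122 | -4.01 |
| 2015 | 10 Mar 2015 | 1 Jul 2015 | -113 | -3.71 |
| 2015 | 31 Mar 2015 | 1 Jul 2015 | -92 | -3.02 |
| 2015 | 30 Jun 2015 | 1 Jul 2015 | -1 | -0.03 |
| 2015 | 1 Sep 2015 | 1 Jul 2015 | +62 | +2.04 |
| Mar 2015 | 1 Mar 2015 | 15 Mar 2015 | -14 | -0.46 |
| Mar 2015 | 10 Mar 2015 | 15 Mar 2015 | -5 | -0.16 |
| Mar 2015 | 31 Mar 2015 | 15 Mar 2015 | +16 | +0.53 |

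**Where the rules fail.** The year-only rule gives a negative value for every first infusion from 1 January to 30 June, which is 181 of the 365 days in 2015. The missing-day rule does so on days 1 to 14 of any month: 14 x 12 = 168 of 365 days, or 46%. These are shares of calendar days, not of patients.

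**Derived value against truth.** Take diagnosis 2015 and first infusion on 10 March 2015. The true diagnosis lies between 1 January and 10 March, so the true duration is 0 to 68 days (68 / 30.4375 = 2.2 months). The derived value is -113 days. The error therefore runs from -113 days (-3.7 months) to -113 - 68 = -181 days (-5.9 months).

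**Effect on a cohort of 6.** The mean shifts by between -3.71 / 6 = -0.6 month and -5.95 / 6 = -1.0 month. The negative value is the minimum unless another patient's is lower. The median is the average of the third and fourth ordered values, so it moves only if at least two other patients have shorter true durations.

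**With the imputed date capped at first infusion.** Every negative value in the table becomes 0. The non-negative values (+62 and +16 days) stay as they are. In the 10 March example the remaining error is 0 to -68 days.

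**The case against.** The strongest reply is that this may never happen. The documents do not say how many diagnosis dates are partial. The 10 March example needs a patient diagnosed within ten weeks of dosing whose month of diagnosis is nonetheless unknown. Since evidence of the diagnosis is an entry criterion, the full date of so recent a diagnosis is probably on file, though that is an inference. Part B patients, and Part A patients without sarcoma, must already have failed standard treatment, which makes the same-month case implausible and the same-year case unlikely for them. All of this stands. A reader might infer that patients dosed before July 2015 are generally affected; the documents support only that a patient meeting these conditions would be.

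The second reply is that a 1 July rule can be about six months wrong in any year (a December 2014 diagnosis recorded as 2014, for example), and the plan accepts that. This also stands as regards precision. The difference is that a negative value is not imprecise but impossible, and it can be prevented without affecting other records.

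The third reply is that a negative duration would be noticed: the table is small, the partial dates are listed, and Protocol 9.1 provides for data checks and a database quality review. That makes an unnoticed error unlikely. It does not supply a rule: a truly year-only date is not itself a data error, so any repair would be improvised once the value had been seen.

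A reader might also infer that the flaw distorts a comparison of the cohorts or shifts the median. The documents do not support this. DLT evaluation is independent by cohort, no covariate adjustment or subgroup analysis is preplanned, and no section uses duration of disease to compare cohorts. A recently diagnosed patient is likely to be at or near the bottom of the ordering already, so the median will usually not move.

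**Conclusion.** The point holds as a minor specification error: the stated rules give an impossible value under definable conditions, and nothing else in the protocol or SAP corrects it.

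- **Size.** For a year-only date with dosing in March 2015, the derived value is -3.0 to -4.0 months. Across January to June 2015 dosing dates the rule can give -1 to -181 days. A missing day alone gives at most -14 days. The values below zero should not be read as the error itself, which is larger by the true duration.
- **Reach.** Only the descriptive summary of duration of disease is affected, mainly its minimum and mean, and mainly for newly diagnosed sarcoma patients in Part A. Duration of disease enters no DLT, PK, safety or efficacy analysis.
- **Assumptions.** At least one such patient has a partial date, and the rule is programmed as written. Frequency cannot be estimated from the documents.

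**What to change.** Add one sentence to SAP 6.3 after the two rules: *An imputed diagnosis date that falls after the first infusion date will be replaced by the first infusion date.*

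This sets the negative values to 0 and leaves all others unchanged. It cannot contradict the known part of the date, because in both cases the first infusion lies in the recorded year or month. A cap at consent lacks that property: with consent on 25 March, diagnosis recorded as April 2015 and first infusion on 10 April, it would move the diagnosis into March. A midpoint rule for all same-year dates would also alter values that are already plausible.

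The cost is one sentence and one line of code. The small downside is that 0 is still an approximation, too low by up to 2.2 months in the 10 March example. The SAP describes two Part A cohorts where the current protocol has three, so the sentence can go into the revision that this difference calls for.

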6.4. Multiple Comparisons/Multiplicity

No adjustments for multiplicity will be made in this study.

6.5. Use of an “Efficacy Subset” of Patients

No particular efficacy subsets will be defined in this study.

6.6. Patient Disposition

Frequency distributions of patients in the Enrolled population, the FAS population or the DLT population (Part A only), will be summarized by part and cohort.

Summary of the screen failure and reason will be provided.

For the Enrolled population, frequency distributions of patients with a specific value for disposition (i.e. completion or discontinuation) will be summarized by part and cohort. Also, frequency distributions of patients who discontinued will also be summarized by part, cohort and reason for discontinuation.

Listing of patient disposition and of primary reason for discontinuation will be provided for the Enrolled population.

6.7. Patient Characteristics

For the FAS population, demographic and baseline disease characteristics will be summarized by part and cohort.

Demographic characteristics are as follows:

age (years), age categories (<65 years vs. ≥65 years), gender, race, height (cm), weight (kg), body surface area (m²) and Body Mass Index (kg/m²),

where body surface area is calculated using DuBois method; $0.007184 \times \text{weight}^{0.425} \times \text{height}^{0.725}$ and Body Mass Index = $\text{weight} / (\text{height} / 100)^2$.

Baseline disease characteristics are as follows:

Alcohol use, Tobacco use, Eastern Cooperative Oncology Group (ECOG) performance status, initial pathological diagnosis (or cancer type), disease stage at diagnosis, TNM at diagnosis, sites of Metastatic Disease, and duration of disease (months from the first confirmation of cancer to the first infusion)

In addition, prior anticancer treatments or surgery (radiotherapy, surgical procedure and systemic therapy), historical conditions and pre-existing conditions will be summarized by part and cohort.

Listings of demographic and baseline disease characteristics, of historical conditions and of pre-existing conditions also will be provided for the FAS population.

6.8. Treatment Compliance

Details are described in Section [6.11.1](#).

6.9. Concomitant Therapy

Concomitant therapies will be categorized using World Health Organization Drug dictionary.

Granulocyte colony stimulating factors (G-CSF) and other concomitant therapies will be summarized by part and cohort for the FAS population, respectively. Listings of G-CSF, other concomitant therapies and transfusion will be provided.

6.10. Efficacy Analyses

6.10.1. Primary Outcomes and Methodology

The objective response rate (ORR) and the disease control rate (DCR) will be primarily evaluated.

The ORR will be calculated as the number of patients who achieve a best overall response (BOR) of complete response (CR) or partial response (PR) using the investigator response assessments, divided by the total number of patients.

The DCR will be similarly calculated as the number of patients who achieve a BOR of CR, PR or stable disease (SD) using the investigator response assessments, divided by the total number of patients.

Patients who do not have a tumor response assessment for any reason are considered as not evaluable (NE) and are included in the denominator when calculating these response rates.

It should be noted that the BOR is determined from the sequence of cycle responses (i.e. responses obtained from the start of the study treatment until the study discontinuation). CR or PR will be claimed only if the criteria for each are met at a subsequent time point (at least 4

weeks). In the case of SD, measurements must have met the SD criteria at least once, at least 6 weeks after the first infusion of the study drug.

For the FAS population, the ORR, DCR and BOR will be summarized by part and cohort with 95% CI using the Wilson formula (Altman et al. 2000; Wilson 1927).

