- The patient has evidence of objective progressive disease by radiological assessments (RECIST version 1.1) or deteriorating clinical symptoms of progressive disease. (Patients with objective progressive disease can be treated continuously based on the clinical symptoms at the discretion of the investigator.)
- The patient experiences unacceptable toxicity.
- The patient is significant noncompliant with study procedures and/or treatment (Section 7.6).
- The patient becomes pregnant.
- Both doxorubicin and olaratumab in Part A or olaratumab in Part B are discontinued (Section 7.2.2.1).

The reason and date of discontinuation will be collected for all patients. The date of discontinuation (for any of the above reasons) from study treatment is to be reported on the case report form (CRF). Patients who discontinue will have follow-up procedures performed as shown in the Study Schedule ([Attachment 1](#)).

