10.6. Efficacy

Efficacy data will be summarized by part and cohort using the FAS population. Efficacy data includes the objective response rate with confirmed partial response (PR) or complete response (CR), and the disease control rate with confirmed PR, CR, or stable disease (SD) as best overall response according to RECIST version 1.1. Progression-free survival and duration of response will also be included in efficacy data.

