- b Vital sign measurements will be obtained prior to and at the completion of each olaratumab administration, and prior to each doxorubicin administration.
- c Vital sign measurements will be obtained prior to and at the completion of olaratumab administration, and approximately one hour following the completion of olaratumab administration.
- d Cohort 1 only.
- e 15 mg/kg in Cohort 1 and 2, and 20 mg/kg as loading dose in Cohort 3.

Study Schedule for Protocol I5B-JE-JGDK – Part A: Cycle 2 and beyond

Relative day within a cycle	Cycle 2-6				Cycle 7-n		Follow-Up ^c	Comments
	1a	2	3	8	1b	8		
Allowance (days)	+3			±3d	+3	±3	±5	
Informed consent	X							Informed consent form signed (prior to beginning of Cycle 2).
Pregnancy test	X ^e				X ^e		X	Should be performed approximately every 6 weeks (i.e., at the beginning of Cycle 3 and every other cycle thereafter) during the study.
Physical examination	X ^e				X ^e		X	Includes medical interview, weight, and body surface area.
Vital signs	X ^f			X ^f	X ^f	X ^f	X	Pulse rate, respiration rate, temperature, and supine blood pressure will be measured.
ECOG performance status	X ^e				X ^e		X	
ECG	See Attachment 4							Obtain ECGs before any associated blood draws.
Echocardiogram	X ^e				X ^e		X	Should be performed locally at Cycles 5 and 7 (within 3 days prior to the treatment on Day 1, but re-measurement is not necessary in case of dose delay of Day 1) and follow-up visit.
Hematology	X ^e			X ^e	X ^e	X ^e	X	
Serum chemistry	X ^e			X ^e	X ^e	X ^e	X	
Coagulation	X ^e				X ^{e,h}		X	
Urinalysis	X ^e				X ^{e,h}		X	Should be performed approximately every 6 weeks (ie, at the beginning of Cycle 3 and every other cycle thereafter).
CTCAE v4.03 grading	X	X ^g	X ^g	X	X	X	X	Throughout study as needed.
Concomitant medications	X	X ^g	X ^g	X	X	X	X	
Radiological tumor assessment	X				X		X	Prior to Cycles 3 and 5 (no more than 14 days prior to Day 1 Cycle 3 and 5), then every 2-4 cycles as clinically indicated.
PK sampling	See Attachment 4							
Immunogenicity plasma sampling	See Attachment 4							
Olaratumab administration	X			X	X	X		
Doxorubicin administration	X	X ^g	X ^g					

Study Schedule for Protocol I5B-JE-JGDK – Part A: Cycle 2 and beyond

Abbreviations: CTCAE = Common Terminology Criteria for Adverse Events; ECG = electrocardiogram; ECOG = Eastern Cooperative Oncology Group; PK = pharmacokinetic.

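### SAP 6.10.1 sets no cut-off at first progression for best overall response, so an SD (less likely a confirmed CR or PR) recorded after progression can enter DCR or ORR

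*SAP*

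**What the plan says.** SAP 6.10.1 names ORR and DCR as the efficacy outcomes evaluated first. Both count patients by BOR on the investigator's assessments: CR or PR for ORR, and CR, PR or SD for DCR. BOR is drawn from the sequence of cycle responses, which the SAP spells out as "responses obtained from the start of the study treatment until the study discontinuation". Two conditions follow. For response, "CR or PR will be claimed only if the criteria for each are met at a subsequent time point", at least 4 weeks on. For stable disease, "measurements must have met the SD criteria at least once, at least 6 weeks after the first infusion of the study drug". Neither condition refers to progression.

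Protocol 6.3.1 lists objective PD as a reason to discontinue and then adds an exception: "Patients with objective progressive disease can be treated continuously based on the clinical symptoms at the discretion of the investigator". Attachment 1 schedules tumor assessments before Cycles 3 and 5 and "then every 2-4 cycles as clinically indicated". It also marks one at the follow-up visit, in both parts.

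Protocol 10.6 describes ORR and DCR with the response categories taken "as best overall response according to RECIST version 1.1". SAP 6.10.1 does not repeat that reference.

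The other two response-based outcomes are tied to progression. PFS (SAP 6.10.2.2.2) ends at the earlier of objective PD and death. Duration of response (SAP 6.10.2.2.3) runs from the first observed response to objective PD.

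**The concern.** A best-of rule depends on where its window closes. Here it closes when the patient leaves the study, and the protocol allows that to come after objective PD with further scans in between. An assessment made after progression therefore falls inside the BOR window as the SAP words it.

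The effect runs one way: adding later assessments to a best-of rule can raise a patient's category but never lower it. It also leaves the efficacy definitions out of step with each other, because one patient could be counted as controlled or responding in DCR or ORR and as progressed in PFS. In groups of about six, a single such patient visibly changes the reported rate.

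**Working it through.** The plan states no ORR, DCR or power figure to reproduce (SAP 5.2 says that the sample size has no power basis). The check therefore sets the rules against the schedule and then sizes one reclassification.

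**Inputs**
- BOR window, confirmation rule, SD rule and Wilson 95% interval: SAP 6.10.1.
- Treatment after objective PD: Protocol 6.3.1.
- Scan times: Protocol Attachment 1, with pre-Cycle 3 and pre-Cycle 5 scans no more than 14 days before Day 1 of the cycle.
- Group size: 6 per Part A cohort and 6 in Part B (SAP 5.2), stated elsewhere as a minimum.

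**Step 1. Can an SD recorded after PD meet the SD rule?** On an undelayed schedule, Day 1 of cycle k is study day 1 + 21(k − 1).
- Cycle 3: 1 + 42 = Day 43, so the first scan falls on Days 29 to 43.
- Cycle 5: 1 + 84 = Day 85, so the second scan falls on Days 71 to 85.
- Six weeks after first infusion is Day 43. The second scan is 70 to 84 days after first infusion, always past that point.

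A patient recorded as PD at the first scan, kept on treatment, and recorded as SD at the second meets the SD rule as written.

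**Step 2. Can a CR or PR recorded after PD be confirmed?** Later scans are 2 to 4 cycles apart, that is 42 to 84 days, against a required 28. The spacing is met, but the patient needs two such assessments after PD. This route is less likely than the SD route, so DCR is more exposed than ORR.

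**Step 3. The same patient under each definition**

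| Outcome | Tied to PD? | Patient with PD first, then SD or confirmed response |
|---|---|---|
| BOR, ORR, DCR (SAP 6.10.1) | No | SD counts in DCR; CR or PR counts in both |
| PFS (SAP 6.10.2.2.2) | Yes | Already progressed at the earlier scan |
| DOR (SAP 6.10.2.2.3) | Yes | For a responder, negative if measured to that PD; undefined if no later PD is named |

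**Step 4. Size of one reclassification.** The rate moves by 1/n: 1/6 = 16.7 points, or 1/7 = 14.3 points if a cohort has 7. The Wilson interval is [p + z²/2n ± z√(p(1 − p)/n + z²/4n²)] / (1 + z²/n), with z = 1.96 and n = 6:

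| Window closed at PD | One post-PD patient counted |
|---|---|
| 0/6 = 0% (0 to 39.0) | 1/6 = 16.7% (3.0 to 56.4) |
| 1/6 = 16.7% (3.0 to 56.4) | 2/6 = 33.3% (9.7 to 70.0) |
| 3/6 = 50.0% (18.8 to 81.2) | 4/6 = 66.7% (30.0 to 90.3) |

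**Step 5. How often?** The documents give no rate. Purely as an assumption, let each patient independently have probability q of a BOR earned only after PD. The chance of at least one in a group of 6 is 1 − (1 − q)⁶: 11.4% at q = 2%, 26.5% at 5%, 46.9% at 10% and 62.3% at 15%.

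**The case against.** The strongest reply is that Protocol 10.6 already governs BOR through RECIST 1.1. A programmer who applies that standard's own window may never meet the problem, and the SAP does not announce a departure from it. This carries weight as to what the sponsor probably intended. It does not settle the text: neither document reproduces that window or states a PD cut-off, and SAP 6.10.1 spells out a different end point without citing the standard. For the same reason, a reader should not go further and infer that the SAP contradicts RECIST 1.1. The documents do not contain what that would need.

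Second, the criteria for SD are not in the documents, so whether a particular scan after PD would be labelled SD rests on the investigator's assessment. This stands, and it is why the point is that such a record can count, not that it will.

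Third, exposure is limited. PD is normally a reason to stop, continuation is an exception, and later scans are as clinically indicated. All of this stands and supports expecting few cases. The follow-up scan does mean that a patient who stops treatment at PD can also have a later assessment inside the window.

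Fourth, the data would be visible. SAP 6.10.2.1 lists the overall response at each assessment, and SAP 6.10.2.2 lists BOR, PFS and DOR by patient. That makes an affected patient easy to find, but it does not correct the summary rate.

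**Conclusion.** The point holds as a defect of definition. As written, the SAP's BOR window admits an SD recorded after PD, or less likely a confirmed CR or PR, into DCR or ORR, and this conflicts with the PD-based definitions of PFS and DOR. Each affected patient raises a rate by 16.7 points in a group of 6. The intervals on either side overlap heavily, as they would for any single patient at that size.

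This rests on reading the SAP sentence literally and on at least one patient being scanned after PD. The number is not given and is probably small.

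Two stronger readings are not supported. A reader might infer from the SAP heading on primary outcomes that a primary conclusion is at risk. However, the primary objectives are safety and tolerability (Part A) and PK (Part B), ORR and DCR are descriptive for a secondary objective, and the preplanned interim analysis in SAP 6.15 is a safety analysis. No test or decision rule uses either rate. A reader might also infer that reported rates will be inflated, but the documents show only that they could be. The correction should be made, but it is not critical.

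**What to change.** In SAP 6.10.1, change the end of the BOR window so that it reads: up to and including the first objectively determined PD, or study discontinuation if earlier. The confirmation and 6-week rules can stay as they are, applied inside that window. A reference there to RECIST 1.1, matching Protocol 10.6, would help but does not replace the clause.

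Nothing else is needed. Assessments after PD remain in the by-assessment response listing of SAP 6.10.2.1. A separate cut-off at new anticancer therapy would add little, because Protocol 7.5 bars other cancer therapy on study, Protocol 6.3.1 stops study drug before another effective agent is introduced, and Protocol 8.1.2.2.3 asks for follow-up assessments before new therapy begins. The protocol's rule on continuing treatment is not affected.

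The cost is one clause and one programming condition, with no new data. The supplied SAP follows the December 2014 protocol and describes only two Part A cohorts, whereas the current protocol has three, so the clause can go into a revision that is due in any case.
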